The current proposal will assess the risks and benefits of the use of oral bisphosphonates to prevent fragility fractures amongst patients with stage \geq 3B CKD. Oral bisphosphonates are the first line therapies for the primary and secondary prevention of osteoporotic fractures, as recognized by NICE guidelines (TA 160 and 161), but they are contraindicated in patients with eGFR<30-35. The drugs assessed will be the currently recommended ones: oral alendronate, risedronate, and ibandronate.

Use of oral bisphosphonates will be identified using pre-specified lists of the British National Formulary (BNF) within CPRD, and Anatomic Therapeutic Classification (ATC) codes for OUHD (Appendix 1).

There is no approved alternative bone medication for patients with severe CKD, and therefore oral bisphosphonate users will be compared to those not on anti-osteoporosis therapy (i.e. drug non-users).

EXPOSURE PERIODS

As the data sources include information on drug prescribing (CPRD) or dispensing (OUHD) as opposed to drug consumption, the prescription duration may not reflect the true number of days over which a prescription was used. As a result, assumptions will be made to account for non-adherence (or non-compliance) in order to define periods of continuous exposure.

We will assume that any overlap between two prescriptions of the same bisphosphonate represent early collection of a repeat prescription. Hence, any overlapping days between two prescriptions of the same drug will be added to the end of the period covered by the two prescriptions. In order to define periods of continuous use of study drugs, any two prescriptions of the same drug will be concatenated if the gap between the end of the first of the two prescriptions and the start of the second of the two prescriptions was less than 30 days apart.

DESIGN AND THEORETICAL/CONCEPTUAL FRAMEWORK

CONCEPTUAL FRAMEWORK

An observational cohort study using routinely collected data will be performed to evaluate the potential risks (CKD progression, hypocalcaemia/hypo-phosphatemia, and a number of adverse events) and benefits (bone density improvement, and fracture protection) observed amongst patients with stage ≥3B CKD in actual 'real life' NHS practice.

STUDY DESIGN

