The chosen study design is a propensity score-matched retrospective cohort study. This is one of the best pharmaco-epidemiological designs available for the assessment of intended (benefits) and unintended (risks) effects of drugs in observational data. Propensity score-matching will therefore be used to match each eligible bisphosphonate user to 5 non-users, producing matched comparable (in terms of observed baseline characteristics) cohorts.

TARGET POPULATION

The target population of this study will be patients with an eGFR<45 (based on serum creatinine) aged 40 years or older at the age of biochemistry testing.

EXCLUSION CRITERIA

From the population described above, we will exclude those with any of the following exclusion criteria:

- Less than 1 year of follow-up data available within the data source/s.
- CPRD participants with no possible linkage to HES.
- Use of anti-osteoporosis medication/s in the previous year (except calcium and/or vitamin D supplements).
- Use of any (except calcium and/or vitamin D supplements) other anti-osteoporosis medication/s (other than bisphosphonates).

SETTING/CONTEXT

Setting: The proposed study will obtain data from both primary (CPRD) and secondary (HES) care.

Study period: Currently used oral bisphosphonates (alendronate, risedronate and ibandronate) were approved and launched to the market in 1996 onwards. Our study period will therefore cover from 1996 to the latest data extraction for the identified data sources, likely 31/12/2014.

Follow-up: Data from randomized placebo-controlled trials have shown that bisphosphonates are effective to reduce fracture risk only after at least 6 months of continuous use (27). That is not the case though for adverse events, which can be observed immediately after bisphosphonate therapy initiation (14, 17, 28). Therefore, different follow-up windows will be established, as follows:

- Safety outcomes (WP1 and WP3): Patients will be followed from the latest of the following dates
- a) Start of study period
- b) One year of valid data in database
- c) Date of incident prescription of bisphosphonate (after one year of non-use)

until the earliest date of:

- a) The end of enrolment in the database (due to moving out or death)
- b) Date of last data update in the database
- c) Stopping of treatment +30 days (no repeat prescription within 1 month)
- d) Switch of treatment to other (non-bisphosphonate) osteoporosis medication

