- e) Outcome of interest (different date for each study outcome)
- Effectiveness outcomes (WP2 and WP4): Patients will be followed from the latest of the following dates
- a) Start of study period
- b) One year of valid data in database
- c) Date of continued prescriptions of an oral bisphosphonate for 6 months after the date of therapy initiation

until the earliest date of:

- a) The end of enrolment in the database (due to moving out or death)
- b) Date of last data update in the database
- c) Stopping of treatment +180 days (no repeat prescription within 6 months)
- d) Switch of treatment to other osteoporosis medication, with no repeat prescription of oral bisphosphonates within the next 6 months
- e) Incident recorded fracture (WP2) or last BMD measurement available (WP4)

SAMPLING

One of the advantages of routinely collected datasets is that the contained information is readily available, not needing active recruitment. Therefore, all patients eligible (see target population and exclusion criteria above) registered in the chosen data sources will be included.

Sample size/power: According to feasibility counts provided by CPRD, the number of eligible patients (with an eGFR<45 and possible to link to HES) would be of 204,528 subjects, and 34,127 (16.7%) of these received oral bisphosphonate prescriptions. These numbers would provide statistical power to reliably answer each of the study aims, as it can be seen below:

Work-package 1: In a survival analysis (log-rank 2-sided test), accepting 5% type I error and 20% attrition from propensity score matching and loss to follow-up in 2 years, and assuming CKD stage progression rates of 12/100 person-years (29), the available number of participants would provide 90% power to detect an excess risk of CKD progression of 10% or more (HR \geq 1.10) associated with oral bisphosphonate use.

Work-package 2: In a log-rank (2-sided) test, and accepting 5% type I error and 20% drop-out, with 2 years of follow-up and an expected fracture rate of 103/10,000 person-years in CPRD data (30), the available sample size would provide 90% power to detect a fracture reduction of at least 15% (HR≤0.85) amongst oral bisphosphonate users (compared to non-users).

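### The WP2/WP4 switch criterion looks ahead: whether time and fractures after a switch to another osteoporosis drug are kept depends on a later prescription

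*Protocol*

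**What the plan says.** All references are to the Protocol.

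- **Setting/Context, Follow-up, effectiveness outcomes (WP2 and WP4).** End criterion d) is "Switch of treatment to other osteoporosis medication, with no repeat prescription of oral bisphosphonates within the next 6 months". End criterion c) is "Stopping of treatment +180 days (no repeat prescription within 6 months". Entry requires six months of continued prescribing of any oral bisphosphonate after initiation.
- **Setting/Context, Follow-up, safety outcomes (WP1 and WP3).** End criterion d) is "Switch of treatment to other (non-bisphosphonate) osteoporosis medication", with no further condition. End criterion c) is "Stopping of treatment +30 days (no repeat prescription within 1 month".
- **The reason for two sets of rules.** "Therefore, different follow-up windows will be established, as follows". The reason given is that fracture benefit appears only after at least six months of continuous use, whereas adverse events can appear at once.
- **Health Technologies Being Assessed.** The comparison is that "oral bisphosphonate users will be compared to those not on anti-osteoporosis therapy".
- **Exposure Periods.** In defining continuous use, "any two prescriptions of the same drug will be concatenated if the gap between the end of the first" "and the start of the second of the two prescriptions was less than 30 days apart".
- **Exclusion Criteria.** Use of any other anti-osteoporosis drug is excluded, with no time window stated.
- **Data Analysis, immortal time bias.** Time before the first bisphosphonate prescription is reclassified as non-use. Time after stopping or switching is not mentioned.

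**The concern.** An end-of-follow-up rule should be decidable from what is known on the day it is applied. WP2/WP4 criterion d) is not. On the day of a switch nobody can say whether follow-up has ended, because that depends on what is prescribed over the next six months. A fracture may happen inside that window, and the fracture may change what is prescribed next. The outcome can therefore influence whether it is itself counted.

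Patients who switch and later return also keep the intervening time on another osteoporosis drug in the oral bisphosphonate group. The hazard ratio for fracture is meant to compare oral bisphosphonate use with no anti-osteoporosis treatment, so that time belongs to neither side. Fracture is the main effectiveness outcome, and the protocol takes care elsewhere to avoid time-related bias.

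**Working it through.** **1. The two switch criteria side by side.** WP1/WP3: a switch to a non-bisphosphonate osteoporosis drug ends follow-up. WP2/WP4: a switch ends follow-up only if no oral bisphosphonate is prescribed in the following six months. The stated reason for separate windows (benefit after six months of continuous use) supports the delayed start in WP2/WP4. It does not bear on how a switch is handled.

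**2. Reading A: the end date is the switch date.** Take two users who switch on the same day and both fracture two months later. The look-ahead window still has 6 − 2 = 4 months to run.

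- User 1 is prescribed an oral bisphosphonate in those four months. Criterion d) is not met, so the fracture counts.
- User 2 is not. Criterion d) is met, follow-up ended at the switch, and the fracture is discarded.

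Up to and including the fracture the two histories are identical. A prescription after the outcome separates them. A third user who switches and dies before returning is cut off at the switch, so staying under observation is also a condition of being retained.

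Let r1 be the probability of returning within the window for switchers who fracture, r0 for those who do not, and p the true fracture risk in the window. Among retained switchers the apparent risk is p·r1 / [p·r1 + (1 − p)·r0], which for small p is about p × r1/r0. If a fracture prompts a return (r1 > r0), retained post-switch time shows too many fractures. If a fracture makes a return less likely (r1 < r0), it shows too few. The protocol gives neither r1 nor r0.

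**3. Reading B: the end date is six months after the switch.** Every switcher then contributes up to six months on another drug, and fractures in that time are credited to oral bisphosphonates. For a user who stops the bisphosphonate at the switch, this date nearly coincides with criterion c) (stopping plus 180 days), so d) would do almost nothing.

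**4. Against the stated comparison.** Under A (for those who return) and under B (for all switchers), the user group includes time on another osteoporosis drug.

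**5. WP2 power, reproduced.** Inputs from Sampling and Study Design: 34,127 users, 20% loss, five non-users per user, 103 fractures per 10,000 person-years, two years, hazard ratio 0.85, two-sided 5%.

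- Users: 34,127 × 0.8 = 27,302. Non-users: five times that.
- Two-year risk: 1 − exp(−2 × 0.0103) = 2.04% in non-users; 1 − exp(−2 × 0.0103 × 0.85) = 1.74% in users.
- Expected events: 3,257. Schoenfeld power: Φ(√(3,257 × 5/36) × |ln 0.85| − 1.96) = 93.3%. Comparison of two proportions: 91.7%.
- Events needed for 90%: 2,865.

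The stated 90% is supported.

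**6. The entry condition.** Exposure Periods joins prescriptions of the same drug less than 30 days apart. WP2/WP4 entry asks for six months on an oral bisphosphonate, not necessarily the same one. A user who moves from alendronate to risedronate at month 4, or who has a 60-day gap, may or may not qualify, depending on which text the programmer follows.

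**The case against.** **Separate windows are declared openly.** This stands for criterion c). A 180-day tail is a stated carry-over window. Its rationale is missing, but it is a design choice and not a contradiction of the 30-day joining rule, which describes how prescriptions are linked rather than when follow-up ends. The planned analysis by medication possession ratio (below 0.4, 0.4 to below 0.8, 0.8 and above) also probes low coverage. Neither point repairs d).

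**The exclusion may make d) moot.** If the exclusion for other osteoporosis drugs covered follow-up, switchers would be removed altogether. But then both switch criteria would have nothing to act on, and patients would be selected on future drug use. A baseline reading is the only one that gives the switch criteria a purpose, and under it the defect remains.

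**Within-class switches.** Exposure Periods does not say that such a switch breaks use, and the safety criterion names only non-bisphosphonate drugs, which points to class-level exposure. This is fair, and it is why the entry condition is a matter of reconciliation and a secondary one.

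**A stronger reading.** A reader might infer that gaps of up to six months make the WP2 estimate something other than an effect of oral bisphosphonate use, or that the study is underpowered. The documents do not support this. They do not say that gap time is treated time, and they give no discontinuation rate or residual effect. Suppose a share f of counted time is off drug with no residual effect, so that the hazard ratio is 0.85(1 − f) + f. Then f = 0.1 gives 0.865 and 87% power, f = 0.2 gives 0.880 and 78%, and f = 0.5 gives 0.925 and 39%. With full residual effect the ratio stays at 0.85 and power at 93%. Every value of f is an assumption, and none of these figures concerns the switch criterion.

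**Conclusion.** The concern holds for WP2/WP4 criterion d). On either reading of its end date the rule is worse than the one already written for WP1/WP3: it makes retention depend on the future, or it counts time on another drug, and it departs from the stated comparison. The conclusion assumes that the exclusion for other osteoporosis drugs applies at baseline.

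The size cannot be calculated without switch and return rates. The direction is also open: r1/r0 may lie on either side of one, and time on another effective drug could add apparent benefit. The argument that the outcome affects its own inclusion applies to WP2. For WP4 the point is limited to bone density change that may include time on another drug.

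The documents support describing the WP2 estimate as one for oral bisphosphonate use with a 180-day carry-over, possibly including some time on another drug. They support nothing stronger. The unreconciled entry definition is a secondary point.

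**What to change.** 1. In WP2/WP4 end criterion d), delete the condition about a repeat oral bisphosphonate prescription. Follow-up then ends at the first prescription of another (non-bisphosphonate) osteoporosis medication, as in the safety criterion.
2. State that the exclusion for use of other anti-osteoporosis drugs applies at baseline.
3. Reconcile the same-drug, under-30-day joining rule with the WP2/WP4 entry condition, so that one definition decides who enters the cohort.
4. The 180-day tail may stay as a declared carry-over window. A 30-day tail as a sensitivity analysis is optional.

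The cost is a few reworded sentences, a re-run of the exposure code and slightly fewer exposed person-years in WP2/WP4. These are analysis definitions on retrospective data and change no patient's care.

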Confounders: pre-defined lists of confounders will be identified for each of the study outcomes. These will be included in separate propensity score logistic equations to minimize confounding by indication. Propensity scores (ps) represent the probability that a patient will receive a specific treatment based on his/her baseline characteristics (5).

Power: according to feasibility counts from CPRD, 4,127 eligible (eGFR<45) bisphosphonate users and 204,528 eligible non-users are available. These numbers provide >90% power to detect as significant a HR of \geq 1.20 for the association between bisphosphonate use and the outcomes in WP1 and WP3, and a HR o \leq 0.85 for the association between bisphosphonate use and fracture risk (WP2). Regarding WP4, the numbers provided by OUHD (>500 bisphosphonate users and >3,000 non-users with eGFR<45 available in the dataset at 31/12/2012) ensure 80% power to detect as significant an expected >25% difference in bone loss between bisphosphonate users and non-users.

Statistical analyses: firstly, logistic equations will be fitted to estimate ps for each of the study outcomes. Secondly, each bisphosphonate user will be ps-matched to 5 non-users using caliper-matching methods. Ps-matching has been shown to be useful to minimize confounding by indication in observational studies involving drugs (i.e.pharmacoepidemiology) (6). Missing confounders will be handle with 10 multiple imputation by chained equations. Finally, time-varying Cox regression models stratified by ps matched sets will be used to study the association between bisphosphonate use and each of the study outcomes in WP1-3; similarly, linear regression modeling will be used to study the relationship between bisphosphonate use and hip bone density change in WP4.

BACKGROUND AND RATIONALE

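### The 90% power stated for WP1 at HR 1.10 does not follow from its own inputs, which give over 99.9% at HR 1.10 and 90% at about HR 1.05; the error is conservative

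*Protocol*

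**What the plan says.** The WP1 paragraph under Sampling, Sample size/power, fixes all the ingredients of a power calculation except the matching ratio:

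- Test: "In a survival analysis (log-rank 2-sided test), accepting 5% type I error".
- Losses and duration: "20% attrition from propensity score matching and loss to follow-up in 2 years".
- Event rate: "assuming CKD stage progression rates of 12/100 person-years".
- Counts, from the paragraph just before: the eligible number "would be of 204,528 subjects, and 34,127 (16.7%) of these received oral bisphosphonate prescriptions".
- Result: the cohort "would provide 90% power to detect an excess risk of CKD progression of 10% or more", that is HR 1.10 or above.

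The Study design section supplies the ratio, five non-users per user.

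The Summary's Power paragraph gives one statement for WP1 and WP3 together: "These numbers provide >90% power to detect as significant a HR of" 1.20 or more. The numbers it refers to are 4,127 users and 204,528 non-users. The body has 34,127 users within a total of 204,528, and the Data collection section also speaks of more than 34,000 users.

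**The concern.** A rate of 12 per 100 person-years over 2 years means that about one patient in five progresses. With some 27,000 users and 136,000 comparators after attrition, that is tens of thousands of events, far more than 90% power at HR 1.10 requires. So either the power figure is wrong, or it was computed from a rate or follow-up other than the one printed.

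What is at stake is modest. The cohort is every eligible patient, so this figure sets no sample size. It is, however, the plan's statement of what its renal-safety comparison can resolve, and a reader cannot reproduce it. The matching sentence in the Summary rests on a different user count, so a correction made in one place only would leave the document inconsistent.

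**Working it through.** **Inputs** (protocol; Sample size/power and Study design): 34,127 users; 5 non-users per user; 20% attrition; 2 years; 0.12 per person-year; two-sided 5%; HR 1.10. I assume a constant hazard, a full 2 years of follow-up and an unmatched log-rank test.

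**Step 1: the plan's own figure.**
- 2-year incidence in non-users: 1 − exp(−0.12 × 2) = 21.3%. In users at HR 1.10: 1 − exp(−0.264) = 23.2%.
- After attrition: users 34,127 × 0.8 = 27,302; non-users 5 × 27,302 ≈ 136,508.
- Events: 27,302 × 0.232 + 136,508 × 0.213 ≈ 35,460.
- Schoenfeld: z = √(35,460 × 1/6 × 5/6) × ln 1.10 = 6.69. Power = Φ(6.69 − 1.96) = 0.999999, against the stated 90%.

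**Step 2: where 90% power falls.** HR = exp[(1.960 + 1.282)/√(35,460 × 5/36)] = 1.047. Power at HR 1.05 is 93%.

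**Step 3: what HR 1.10 needs.** Events = (3.242/ln 1.10)² ÷ (5/36) ≈ 8,330. At 21.3% incidence that is about 6,510 users after attrition, or 8,130 before it.

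**Step 4: Table 1.** In the HR 1.1 column, users × incidence is nearly constant: 330,529 × 0.5% = 1,653; 165,288 × 1% = 1,653; 41,357 × 4% = 1,654. Scaling to 21.3% gives 1,653/0.2134 ≈ 7,750 users, and 34,127 is 4.4 times that. If the table leaves out attrition, 7,750/0.8 ≈ 9,690, still well below 34,127.

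**Step 5: the incidence that would fit 90%.** Table 1 scaling: 1,653/34,127 = 4.8%. Schoenfeld: about 5%. Either is about 2.5 per 100 person-years, not 12.

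**Step 6: alternative readings.** Power at HR 1.10 with 34,127 users, each change made alone unless stated:

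| Reading | Power |
|---|---|
| 1:1 matching | 99.9% |
| 1 year of follow-up | 99.8% |
| 6 months of follow-up | 94% |
| Attrition applied twice | over 99.9% |
| 80% attrition | 92% |
| 12% taken as the 2-year incidence | 99.9% |
| 12% as 2-year incidence, 1:1 and attrition twice, together | 93% |
| Rate misread as 12 per 1,000 | 60% |

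Freedman's formula and a two-proportion test on the stated inputs also give essentially 100%. None of the readings tried returns 90%.

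**Step 7: the Summary's count.** With 4,127 users at 1:5 and the other WP1 inputs unchanged, power is about 22% at HR 1.05, 64% at HR 1.10 and 99% at HR 1.20. With all 204,528 taken as non-users, it is about 71% at HR 1.10. The body's percentage supports the larger count: 34,127/204,528 = 16.7%.

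**The case against.** The strongest reply is that the statement is true as a floor. A cohort with more than 99.9% power at HR 1.10 certainly has 90%, and the figure drives no decision. That stands, and it is why this is a minor point. It does not make the printed figure right: WP1 gives a plain 90%, whereas the WP3 paragraph and the closing power summary use inequality signs.

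A second reply is that the recomputed HR is optimistic. Safety follow-up ends 30 days after treatment stops, which would reduce events. A full 1:5 match would also need 5 × 34,127 = 170,635 non-users, when only 204,528 − 34,127 = 170,401 remain. The second point is negligible: using the actual counts gives 1.048. The first is fair and belongs in the restated sentence, but the paragraph says 2 years, and even 6 months for everyone gives about 94%.

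Three stronger readings are tempting, and the protocol supports none of them.

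- *That the Summary's HR 1.20 is a false WP1 figure.* It is a joint floor of more than 90% for WP1 and WP3, and it equals the WP3 value in the body. It is looser than the WP1 figure, not contradictory.
- *That the plan misstates the smallest effect WP1 would call significant.* It gives no such figure. The HR detectable with 90% power (about 1.05) differs from the smallest observed HR that reaches p < 0.05 (about 1.03 on these inputs).
- *That the WP1 confidence interval must be judged against 1.10.* The protocol does not call 1.10 a margin of importance. It already plans hazard ratios with 95% intervals and Rosenbaum bounds for unobserved confounding. Such a rule would be a preference, not a consequence of the arithmetic.

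**Conclusion.** The WP1 power statement is arithmetically wrong. Its inputs give over 99.9% power at HR 1.10, not 90%, and reach 90% at about HR 1.05. Table 1 confirms the direction and the rough size. A figure of 90% at HR 1.10 would fit a 2-year incidence near 5%, about a quarter of the 21.3% that the stated rate implies.

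The error is conservative: WP1 is not underpowered, and no data, analysis or conclusion changes. The value of 1.05 rests on a constant hazard of 12/100 person-years, a full 2 years of follow-up, a near-complete 1:5 match and an unmatched log-rank test. Shorter on-treatment follow-up would move it upwards, for example to 1.065 with 1 year for everyone.

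The Summary needs attention for a related reason. Its 4,127 users conflict with 34,127 in the body, and with the smaller number the body's HR 1.10 claim would fail. The 16.7% figure and the Data collection section suggest that 4,127 is a slip, but the protocol has to settle it.

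**What to change.** 1. In Sample size/power, Work-package 1, state the power as over 99% at HR 1.10, with 90% reached at about HR 1.05, assuming 12/100 person-years and a full 2 years of follow-up. Add that it is lower if censoring 30 days after treatment stops shortens follow-up. If another rate or duration was used, print that one and the power that follows from it.
2. In the Summary's Power paragraph, first reconcile 4,127 users and 204,528 non-users with the body's 34,127 users among 204,528 eligible patients. Only then give the WP1 detectable HR, separately from WP3's 1.20. The order matters: beside an uncorrected 4,127, HR 1.05 would have about 22% power.

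The cost is wording in two places, with no change to data or analysis.

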Work-package 3: In a log-rank 2-sided test with an alpha risk of 0.05, and assuming a 20% dropout rate, the number of patients available would provide >90% power to detect as significant a \geq 20% excess risk (HR \geq 1.20) for any clinical event with a cumulative incidence of \geq 2% in 2 years follow-up. Less common adverse events or weaker associations would require bigger numbers (Table 1).

Table 1. Number of eligible bisphosphonate users needed to ensure 90% statistical power to			
detect as significant the described associations in a 2-sided survival model (log-rank test),			
assuming 5 bisphosphonate non-users will be matched to each user.			

2-year cumulative					
incidence of adverse					
event/s	HR 1.1	HR 1.2	HR 1.3	HR 1.4	HR 1.5
0.50%	330,529	86,234	39,840	23,218	15,353
1%	165,288	43,130	19,929	11,617	7,683
2%	82,667	21,578	9,974	5,817	3,849
3%	55,217	14,394	6,657	3,883	2,570
4%	41,357	10,802	4,997	2,917	1,932
NOTE : cells in bold indicate characteristics of associations we would have 90% power					
to detect					

The incidence of each of the identified adverse events amongst bisphosphonate users is as follows:

- a) Upper gastro-intestinal events: according to data from the pivotal randomized trial for oral alendronate, 11% of the patients allocated to the active treatment arm developed upper gastro-intestinal events, with 1.6% developing serious events (perforation/ulcer/bleeding) (31);
- b) Hypocalcaemia/hypophosphatemia: although the incidence of bisphosphonateinduced hypocalcaemia/hypophosphatemia in the target population (stage ≥3 CKD

patients) is unknown, data from the UK Renal Registry 2013 report suggest that hypocalcaemia and hypophosphatemia are relatively frequent in end-stage renal disease, with a prevalence of 11% and 12% amongst patients on haemodialysis respectively. In addition, data from cancer patients suggest that 8% of them develop hypocalcaemia requiring medical attention following an infusion of intravenous zoledronic acid (13);

c) Acute kidney injury (AKI): the population-based incidence of AKI has been estimated at 209 cases per million person-years (32), therefore making a 2-year cumulative incidence of 0.04%. Therefore, the available sample size would ensure power to detect as significant an excess risk of ≥40% (HR ≥1.4) of AKI associated with bisphosphonate use. It is however well known that the risk of AKI is higher amongst patients with previous CKD (33).

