In summary, the proposed study would have \geq 90% power to detect as significant an excess risk of \geq 10% between bisphosphonate use and both upper GI and hypocalcaemia/hypophosphatemia events, and of (in the most conservative scenario) \geq 40% between use of bisphosphonates and risk of AKI.

Work-package 4: The Danish OUHD included 35,025 patients in the year 2012. We expect to identify at least 500 CKD patients defined as oral bisphosphonate users, matched 1:5 to 2,500 non-users. Accepting type I error of 5% in a two-sided test, and a common mean (standard deviation) hip BMD loss of 0.61% (1.23%) per year (34), this sample size would provide >80% power to detect as significant a >25% difference in bone loss change between bisphosphonate users and non-users.

DATA COLLECTION

Data linkage and management: As stated above, one key advantage of routinely collected data is the immediate access to large and representative samples of patients with no need for prospective data collection. In our proposal, over 200,000 eligible patients (with an eGFR<45) have been identified in CPRD, with >34,000 of them starting bisphosphonate use in the study period.

More challenging is however the workload involved in the linkage and data management required for the current study, where 2 different data sources (CPRD and HES) will be linked to answer the aims of WP1-3. For this reason we have included co-applicants with extensive experience in linkage between these data sources as described above (see "Response to feedback points"). The data management needed to produce a final working dataset will be carried out by a senior data manager at Oxford with expertise in such procedures. With supervision from the PI and the appointed statistician, she will develop ad-hoc code in Python and SQL to produce a dataset that can be analyzed using standard statistical packages such as Stata.

For WP4, investigators at the Odense Patient Data Exploratory Network (OPEN) initiative will carry out the linkage of clinical (including bone mineral density), biochemistry (i.e. serum

creatinine), and pharmacy dispensations data, as well the needed data management. The funding for these are either included in the requested data license fee (linkage and data management) or provided at no cost by external collaborators (supervision by [name] and [name]).

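### The 90% power claimed for a 40% excess of acute kidney injury does not follow from the protocol's own 2-year incidence of 0.04%, at which power is roughly 20–30%

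*Protocol*

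**What the plan says.** The relevant text is in the Protocol, Sampling, Sample size/power, Work-package 3.

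- **Test and dropout.** "In a log-rank 2-sided test with an alpha risk of 0.05", "assuming a 20% dropout rate".
- **Available users.** Of 204,528 eligible patients, "34,127 (16.7%) of these received oral bisphosphonate prescriptions". Table 1 is built "assuming 5 bisphosphonate non-users will be matched to each user".
- **Table 1.** It gives the users needed for 90% power. The lowest incidence row is 0.50%, where HR 1.4 needs 23,218 users and HR 1.3 needs 39,840.
- **AKI, item c).** "the population-based incidence of AKI has been estimated at 209 cases per million person-years", "therefore making a 2-year cumulative incidence of 0.04%. Therefore, the available sample size would ensure power to detect as significant an excess risk of" 40% or more (HR 1.4 or above). The next sentence adds that AKI risk is higher in people who already have CKD, without giving a rate.
- **Summary after item c).** It claims at least 90% power for all three adverse-event groups, with the 40% excess for AKI described as holding "in the most conservative scenario".

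**The concern.** Item c) states an incidence and then presents the power claim as its consequence. Table 1 stops at 0.50%, so no cell covers 0.04%. The text just above the table warns, correctly, that "Less common adverse events or weaker associations would require bigger numbers (Table 1"). An event more than ten times rarer than the lowest row should need far more users than that row asks for, yet the claim is one that the 0.50% row would support.

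AKI is one of the three named safety outcomes of Work-package 3, and the results are meant for regulators and NICE as possible grounds for changing restrictions on use. A reader who accepts 90% power would take a non-significant AKI result as good evidence against a 40% excess. Whether that reading is safe depends on the incidence, and at the only incidence the protocol gives it is not.

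**Working it through.** **Inputs (all from the protocol).** Users 34,127, or 34,127 × 0.8 = 27,302 after 20% dropout. Five non-users per user (user share 1/6). Two-sided alpha 0.05. HR 1.4. AKI rate 209 per million person-years. The user count is internally consistent: 34,127 / 204,528 = 16.7%. The Summary of Research prints 4,127 users instead. That figure is not used here, and it would lower power further, to about 6%.

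**Step 1: the incidence.** 209 / 1,000,000 × 2 years = 0.0418%. The stated 0.04% is right.

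**Step 2: reproduce Table 1.** Let p2 be the non-user 2-year risk, p1 = 1 − (1 − p2)^HR the user risk, and p̄ = (p1 + 5·p2)/6. The pooled two-proportion formula is

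n = [1.96·√(p̄(1 − p̄)·1.2) + 1.2816·√(p1(1 − p1) + p2(1 − p2)/5)]² / (p1 − p2)²,

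divided by 0.8 for dropout. It reproduces all 25 cells of Table 1 within 0.9%. For HR 1.4 at 0.50% it gives 23,037 against the printed 23,218. The table therefore already includes the 20% dropout and can be compared directly with 34,127.

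**Step 3: users needed at 0.04%.** In Table 1 the number needed is almost inversely proportional to incidence. For HR 1.4 it is 23,218 at 0.50%, 11,617 at 1% and 5,817 at 2%. Scaling gives 23,218 × 0.50/0.04 = 290,225 users. The formula of step 2 gives about 288,000. The shortfall is 290,225 / 34,127 = 8.5-fold.

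**Step 4: power at 0.04%, Table 1 method, after dropout.** p2 = 0.000400, p1 = 0.000560, difference 0.000160. With 27,302 users, the standard error is 0.0001369 under the null and 0.0001531 under the alternative.

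Power = Φ[(0.000160 − 1.96 × 0.0001369) / 0.0001531] = Φ(−0.71) = 24%.

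**Step 5: cross-check by Schoenfeld's formula.** Expected events = 27,302 × (0.000560 + 5 × 0.0004) = 69.9. Power = Φ[√(69.9 × 5/36) × ln 1.4 − 1.96] = 18%. For 90% power about 669 events are needed.

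| Method, HR 1.4 at 0.04% | 20% dropout | No dropout |
|---|---|---|
| Table 1 method | 24% | 28% |
| Freedman, unequal allocation | 21% | 26% |
| Schoenfeld | 18% | 21.5% |

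Using 0.0418% in place of 0.04% adds about one percentage point or less. The HR detectable with 90% power after dropout is about 2.3 (Table 1 method) to 2.6 (Schoenfeld).

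**Step 6: what incidence would support the claim.** The protocol gives no other AKI rate, so the incidences below are assumptions (Table 1 method, 20% dropout, HR 1.4).

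| 2-year incidence | Power |
|---|---|
| 0.04% (protocol) | 24% |
| 0.1% | 46% |
| 0.2% | 72% |
| 0.34% | 90% |
| 0.5% | 97% |

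The threshold of about 0.34% is 0.34/0.04 = 8.5 times the stated figure. By Schoenfeld with dropout it is 0.38%.

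**Step 7: where HR 1.4 does fit.** At 0.50%, 34,127 users exceed the 23,218 needed for HR 1.4 but fall short of the 39,840 needed for HR 1.3. The AKI claim is what that row supports, and 0.50/0.04 = 12.5.

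**The case against.** The strongest reply is that 0.04% is a general-population figure, whereas the cohort has eGFR below 45 and is aged 40 or over. The protocol itself says AKI risk is higher in CKD. If the cohort's 2-year risk is about 0.34% or more, the claimed power is met. This stands as a limit on the consequence. A reader might infer that the study is underpowered for AKI, or that a null AKI result would necessarily give false reassurance. The documents support neither, because they contain no CKD-specific rate.

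It does not rescue the sentence as written. The power claim is drawn from 0.04%. The CKD remark comes afterwards and has no number attached. Calling the claim the most conservative scenario points to the figure without any uplift, which is where it fails.

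A reader might also infer that the 0.50% row was read by mistake, or that a decimal slipped (at 0.4% the Table 1 method needs about 28,800 users, which would fit). Either is possible, but the protocol does not say how the figure arose. Only the mismatch is established.

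Two further points are fair. Hazard ratios with 95% confidence intervals are already planned for every outcome, so no analysis is missing. All eligible patients in the database are included, so correcting the figure changes no sample size, endpoint or model.

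**Conclusion.** The point holds as an error in a stated power figure. At the protocol's own incidence, power for HR 1.4 is roughly 20–30% depending on formula and dropout (24% by the Table 1 method with dropout, 18% by Schoenfeld), against the 90% claimed. None of the formulas tried comes near 90%. The result rests on 34,127 users, full 1:5 matching, two years of follow-up and 20% dropout, all taken from the protocol.

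What is shown is that the derivation fails. Whether the study can detect a 40% excess of AKI depends on an incidence that the protocol does not give. If it is near 0.04%, a true 40% excess would be missed about three times in four, and a non-significant result would not exclude it.

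**What to change.** In item c) and in the Work-package 3 summary, replace the AKI claim with figures from a single method. Mixing formulas would create a new inconsistency: 0.34% gives 90% power by the Table 1 method but only 86% by Schoenfeld after dropout. Suggested text (Table 1 method, 20% dropout):

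*At a 2-year AKI incidence of 0.04% the study has about 24% power for HR 1.4, and the HR detectable with 90% power is about 2.3. At assumed incidences of 0.1%, 0.2% and 0.5%, power for HR 1.4 is about 46%, 72% and 97%; 90% is reached only at about 0.34% or more.*

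Delete the most-conservative-scenario label, or keep the HR 1.4 claim and justify a CKD-specific 2-year incidence of at least about 0.34%. Add that a non-significant AKI result will be read from its confidence interval and does not by itself exclude a 40% excess. The sentence above Table 1 about rarer events needing bigger numbers is correct and stays.

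The cost is wording only. A stated figure becomes less favourable; no data, endpoint or analysis changes.
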